Primary Endpoint	
Anesthetic stability, measured by the variability of the Bispectral Index of the EEG

Secondary Endpoint	
Quality of recovery using the PQRS scale

Intervention	
Deep neuromuscular blockade reversed with sugammadex.

Can adequacy of anesthesia depth and quality of recovery be influenced by the level of neuromuscular blockade?

3. Abbreviations

AE	Adverse event
ALT	Alanine transaminase
AST	Aspartate aminotransferase
BIS	Bispectral Index
CEIC	Portuguese Central Ethics Committee "Comissão de Ética para a Investigação Clínica"
CIOMS	Council for International Organizations of Medical Sciences
CNPD	Portuguese Data Privacy Agency "Comissão Nacional de Protecção de Dados"
DSUR	Development Safety Update Report
ECI	Event of Clinical Interest
eCRF	Electronic Case Report Form
EMG	Electromyography
GCP	Good Clinical Practice
IB	Investigator's Brochure
ICH	International Conference of Harmonization
IMP	Investigational Medicinal Product
Infarmed	Portuguese Regulatory Authority "Instituto da Farmácia e do Medicamento"
MAP	Mean Arterial Pressure
NIMP	Non Investigational Medicinal Product

Can adequacy of anesthesia depth and quality of recovery be influenced by the level of neuromuscular blockade?

NMB	Neuromuscular blockade
PQC	Product Quality Complaint
PQRS	Physician Quality Reporting System
PTC	Post Tetanic Count
SAE	Serious adverse event
SMP	Summary of Product Characteristics
SUSAR	Serious Unexpected Suspected Adverse Reaction
TCI	Targeted controlled infusion
TOF	Train-of-four
ULN	Upper Limit Normal

4. Background and rationale

The Bispectral Index (BIS) of the electroencephalogram (EEG) uses a four-electrode sensor placed on the forehead and is widely used as a quantifiable measure of depth of sedation and depth of anesthesia (DOA) [1-3]. Currently all DOA monitors are EEG based and use indexes similar to the BIS. Scientific evidence for the benefits of BIS guided anesthesia are abundant [4]. Insufficient anesthesia may cause Intraoperative awareness, which may be prevented by maintaining BIS values between 40 and 60 [5-7]. Excessive anesthesia, namely BIS below 45 or 40, is being increasingly associated with increased mortality at one or more years following surgery [8,9], especially if combined with hypotension [10]. Therefore, guiding anesthesia aiming at maintaining BIS within the recommended range offers important advantages. According to a recent NICE report it is also cost effective [11].

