The primary hypothesis is that there is a better anesthetic stability in the deep NMB group (Group 2) and that this is translated as a reduction of the BIS signal variability and a reduction in the required effect-site concentrations of propofol and remifentanyl (representative of the total drug consumption).

b) Secondary objectives

As a secondary objective, we will study the quality of recovery using the PQRS scale to see if maintaining a deep NMB level during surgery has an impact on the patients' quality of recovery.

The secondary hypothesis is that the quality of recovery (PQRS test) is better in the patients of Group 2.

Can adequacy of anesthesia depth and quality of recovery be influenced by the level of neuromuscular blockade?

6. Study design

Patients subjected to anterior cervical spine surgery under general intravenous anesthesia will be randomized to receive one of two protocols regarding the neuromuscular blockade:

- Group 1 – Standard Clinical Practice Group - standard NMB, with a standard rocuronium dose for intubation (0.6 mg/kg). If required, the reversal of neuromuscular block is performed with neostigmine.
- Group 2 – Deep NMB group - with a standard rocuronium dose for intubation (0.6 mg/kg), followed by a constant infusion of rocuronium (10-15 µg/kg/min) to guarantee a PTC less or equal to 2 on the TOF monitor (PTC is evaluated every 5 minutes). The reversal of neuromuscular block is performed with Sugammadex (4 mg/kg).

a) Primary Endpoints

- BIS signal variability using the measured standard deviation during the maintenance phase of anesthesia
- Required effect-site concentrations of remifentanyl and propofol

b) Secondary Endpoints

- PQRS results at 15 and 40 minutes after surgery (taking into account the patient baseline values of the PQRS test done on the pre-anesthetic visit)
- PQRS results at day 3 after surgery

c) Study type

This is an interventional, phase 4, double-arm, parallel, randomized, open-label, single-center study aiming to compare two anesthesia protocols.

Can adequacy of anesthesia depth and quality of recovery be influenced by the level of neuromuscular blockade?

d) Study Timeline

- Study Start Date: April 2016
- Study End Date: April 2017
- First Patient In: April 2016
- Last Patient In: April 2017
- Last Patient Out: April 2017
- Study Analysis: May 2017
- Publication: November 2017

Can adequacy of anesthesia depth and quality of recovery be influenced by the level of neuromuscular blockade?

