e) Flow-chart

Assessment Title	Pre-anesthesia	Anesthesia procedure during surgery	15 minutes PQRS Test	40 minutes PQRS test	Follow-up
Assessment Number	Assessment 1	Assessment 2	Assessment 3	Assessment 4	Assessment 5
Scheduled Day	One the day before surgery	Day 1, time 1	Day 1, time 2: 15 minutes after surgery	Day 1, time 3: 40 minutes after surgery	3 days after surgery
Scheduling Window		>90 minutes	±5 minutes	±5 minutes	±1 days
Informed Consent	X				
PQRS test	X		X	X	X
Medical History	X				
Entry Criteria	X	X			
(Serious)Adverse Events	X	X	X	X	X
Physical Examination	X				
Patient Data online recording		X			
Patient randomization		X			
Patient Satisfaction evaluation					X
Dispense Trial Medication		X			
Pregnancy test	x				

Can adequacy of anesthesia depth and quality of recovery be influenced by the level of neuromuscular blockade?

f) Randomization and blinding procedures

This will be an interventional, randomized and unblinded study, performed at a single center (Centro Hospitalar do Porto).

Patient randomization will be done by a computer software programmed with a varying block randomization technique (to ensure sample size due to the small number of patients in each group), using a uniform distribution. The software will be installed in the data collection computer, and the anesthesiologist will only know to which group the patient was randomly assigned before induction starts. Although block randomization is used, the computer software does not display information about the block assignment of future patients to the user. The software is programmed using the Statistical toolbox of MATLAB.

g) Treatment

Trial participants will be randomly assigned (using varying block randomization) to one of two groups:

- Group 1 – Standard Clinical Practice Group - standard NMB, with a standard rocuronium dose for intubation (0.6 mg/kg). If required, the reversal of neuromuscular block is performed with neostigmine.
- Group 2 – Deep NMB group - with a standard rocuronium dose for intubation (0.6 mg/kg), followed by a constant infusion of rocuronium (10-15 µg/kg/min) to guarantee a PTC less or equal to 2 on the TOF monitor (PTC is evaluated every 5 minutes). The reversal of neuromuscular block is performed with Sugammadex (4 mg/kg).

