- Syringe pump attached to the Fresenius Base Primea for the continuous infusion of rocuronium

Anesthesia Protocol

The anesthesia protocol is as follows:

Can adequacy of anesthesia depth and quality of recovery be influenced by the level of neuromuscular blockade?

- Baseline Mean arterial pressure is noted
- Induction is performed with target effect site concentration of remifentanyl of 3 ng/ml and a constant 1% propofol infusion of 3,3 ml/kg/h until loss of consciousness
- Loss of consciousness is assessed using the standard method of loss of response to name calling and tapping on the forehead
- At loss of consciousness, the propofol effect-site concentration is noted and the TCI propofol target set to 25% of that concentration and then adjusted to maintain BIS between 40 and 60.
- TOF Watch monitor is calibrated according to manufactures instructions and the specifications of GCP of NMB monitoring [21]
- A bolus dose of rocuronium of 0.6 mg/kg is given, this dose is 2xED95 of rocuronium, to allow for tracheal intubation
- After tracheal intubation the muscle relaxant rocuronium administration protocol is performed according to the group the patient was assigned to (Group 1 or Group 2)
- During the procedure the remifentanyl and propofol target concentrations are titrated to achieve and maintain a the BIS value between 40 and 60 (the BIS alarms are be activated in the monitor) and the Mean Arterial Pressure (MAP) between [-30% +30%] of the baseline

At the end of surgery the NBM reversal protocol is as follows:

- Group 1: Propofol infusion is stopped after the surgical dressing, if TOF<90 then neostigmine (40 µg/kg) plus atropine (20 µg/kg) are administered;
- Group 2: Propofol infusion is stopped after the surgical dressing and 4 mg/kg dose of Sugammadex is administered.

In both groups:

- time of recovery of consciousness is recorded
- time of extubation is recorded

Can adequacy of anesthesia depth and quality of recovery be influenced by the level of neuromuscular blockade?

- the post-operative analgesia is with iv paracetamol and iv parecoxib, and iv morphine if required

Monitoring during surgery

During the anesthesia procedure and for both groups of patients, the response protocols to BIS and MAP deviations from the target range are as follows:

Response Protocol to BIS values above 60:

- If EMG activity is present, the remifentanil effect-site target concentration is increased by steps of 1,5 ng/ml until a maximum of 15 ng/ml;

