Where the determination of AE severity rests on medical judgment, the determination of severity must be made with the appropriate involvement of a medically-qualified investigator.

Can adequacy of anesthesia depth and quality of recovery be influenced by the level of neuromuscular blockade?

The severity of AEs will be graded according to the following definitions:

Mild: awareness of sign, symptom, or event, but easily tolerated;

Moderate: discomfort enough to cause interference with usual activity and may warrant intervention;

Severe: incapacitating with inability to do normal daily living activities or significantly affects clinical status, and warrants intervention;

Assessment of Causality

A medically qualified investigator must assess the relationship of any AE (including SAEs) to the use of the investigational product, as unlikely related, possibly related, or probably related, based on available information, using the guidelines listed below:

Unlikely related: no temporal association, or the cause of the event has been identified and attributed to other disease or drug; or the drug, biologic, or device cannot be implicated based on available information;

Possibly related: temporal association, but other etiologies are likely to be the cause; however, involvement of the drug, biologic, or device cannot be excluded based on available information;

Probably related: temporal association, other etiologies are possible, but unlikely based on available information.

Can adequacy of anesthesia depth and quality of recovery be influenced by the level of neuromuscular blockade?

11. Statistics

a) Methods

Differences in age, weight, and height between the groups will be analyzed with t-test.

Continuous data will be analyzed using independent samples t test, or RM ANOVA for repeated measurements.

Univariate analyses will be conducted using chi-square analysis or Fisher exact test where appropriate, to analysis de PQRS recovery result at discrete time points, and repeated measures ANCOVA for continuous data.

Statistical analysis of the subcategories of the PQRS test will be performed using the Cochran Mantel – Haenszel test on the proportions of recovery for each group with continuity correction over two measurement periods.

b) Number of participants

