Sample size calculation with a power of 0.80 and an α of 0.05, considering the primary hypothesis of a reduction in the BIS variability (measured as the standard deviation) and a reduction in the propofol and remifentanil drug consumption (measured as the average effect-site concentration required) during maintenance of anesthesia.

To estimate the standard deviation of our population, we searched our database for standard clinical practice cases with: online data recording; cervical spine surgery; BIS average values within the recommended target values [40-60]; TCI anesthesia with propofol and remifentanil.

A total of 12 patients data were analyzed (mainly due to the lack of online recording during the procedures), the average BIS standard deviation was 8.7 ± 3.14 , and the average propofol and remifentanil effect-site concentrations were 2.68 ± 0.9 $\mu\text{g/ml}$ and 2.83 ± 0.8 ng/ml , respectively.

Can adequacy of anesthesia depth and quality of recovery be influenced by the level of neuromuscular blockade?

A 25% reduction on the BIS variability (standard deviation) was considered clinically relevant, and gave a minimum sample size of 26 per group.

A reduction on propofol average effect-site concentration of 20% was considered clinically relevant, and gave a minimum sample size of 34 per group.

A reduction on remifentanil average effect-site concentration of 20% was considered clinically relevant, and gave a minimum sample size of 24 per group.

Considering the above results and the possibility of patient exclusion due to external complications during surgery, a total of 35 patients per group will be included in the study.

The secondary variable, result of the PQRS test was not used in the sample size calculation, since there are no studies on the comparison of recovery after two different interventions and the data regarding sample calculation that the authors of PQRS showed us are for the recovery at 3 days post-surgery, which is not comparable to our study. Therefore we did not consider adequate to estimate a percentage difference for which we do not know the clinical reality.

The surrogate variables, consumption of ephedrine and labetalol will be analyzed since these drugs are used in the response protocol to target deviations, but they are not considered for the sample size calculation.

c) Level of statistical significance

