The sample was calculated at a significance level of 95%. A p-value below 0.05 is considered statistically significant.

d) Study termination

Data analysis is planned for the end of the trial. No early study termination is planned.

Can adequacy of anesthesia depth and quality of recovery be influenced by the level of neuromuscular blockade?

e) Missing data

Participants with missing primary endpoint data will not be included in the analysis.

f) Deviations

Any change to the statistical plan will be submitted to the competent authorities prior to its implementation.

g) Inclusion in analysis

All data will be included for the analysis (Intention to treat).

Can adequacy of anesthesia depth and quality of recovery be influenced by the level of neuromuscular blockade?

12. Direct access to source documents

The investigator will grant direct access to paper and/or electronic documentation pertaining to the clinical study (e.g. CRFs, source documents such as hospital patient charts and investigator study files) to authorized individuals, as the clinical trial monitors, auditors or health authority inspections. The objective of these accesses is to ensure the trial is being conducted according to local laws and regulations and ICH-GCP.

All site facilities related to the study conduct can be visited during an audit (e.g. pharmacy, laboratory, archives).

The investigator agrees to co-operate and provide assistance at reasonable times and places with respect to any monitoring or auditing activity.

Can adequacy of anesthesia depth and quality of recovery be influenced by the level of neuromuscular blockade?

13. Quality control and quality assurance

The study will be conducted in accordance with the current approved protocol, ICH GCP, relevant regulations and standard operating procedures.

Regular monitoring will be performed according to ICH GCP. Data will be evaluated for compliance with the protocol and accuracy in relation to source documents. Following written standard operating procedures, the monitors will verify that the clinical trial is conducted and data are generated, documented and reported in compliance with the protocol, GCP and the applicable regulatory requirements.

Inspections and Audits

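### The sidedness of the test for average propofol concentration is not stated, and power at 35 per group depends on it (about 79% one-sided, 69% two-sided); age, already collected, is left out of the outcome comparison

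*Combined protocol and SAP*

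**What the plan says.** Section 6 a) lists BIS variability and "Required effect-site concentrations of remifentanyl and propofol" as primary endpoints. The synopsis gives only one: "Anesthetic stability, measured by the variability of the Bispectral Index of the EEG".

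Section 11 b) derives a size for each of three measures at 80% power and alpha 0.05: 26 per group for BIS variability, 24 for remifentanil, and for propofol "A reduction on propofol average effect-site concentration of 20% was considered clinically relevant, and gave a minimum sample size of 34 per group". It then sets 35 per group, citing possible exclusions.

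Section 11 a) gives the test: "Continuous data will be analyzed using independent samples t test, or RM ANOVA for repeated measurements". No covariate is named. A repeated measures ANCOVA appears only in the sentence on PQRS, also without a covariate. It does not reach an average that has one value per patient. Section 11 c) adds: "A p-value below 0.05 is considered statistically significant". Sections 11 a) to c) do not mention sidedness, although the hypothesis in section 5 a) is directional.

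Age enters the analysis once: "Differences in age, weight, and height between the groups will be analyzed with t-test". The plan does not say what follows if the groups differ.

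**The concern.** Two choices are left open for the measure that set the sample size.

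The first is sidedness. A result with a two-sided p-value between 0.05 and 0.10 in the expected direction would be positive on one reading of section 11 c) and negative on the other. The stated power is also not the same claim on the two readings.

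The second is the use of age. Eligible patients are 18 to 80 years old, and age is fixed before randomisation. Section 4 says that effect-site concentrations already reflect gender, weight and height; it does not list age. If age is related to the outcome, leaving it out gives up precision. A baseline t-test on age does not recover that precision, and it invites a decision on adjustment after the data are seen.

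**Working it through.** **Inputs, all from section 11 b).** Propofol 2.68 ± 0.9 µg/ml, 20% reduction. BIS SD 8.7 ± 3.14, 25% reduction. Remifentanil 2.83 ± 0.8 ng/ml, 20% reduction. The means and SDs come from 12 standard-practice patients. Alpha is 0.05, target power 0.80, and 35 per group are enrolled.

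**Standardised differences.**
- Propofol: 0.2 × 2.68 / 0.9 = 0.536 / 0.9 = 0.596
- BIS SD: 0.25 × 8.7 / 3.14 = 2.175 / 3.14 = 0.693
- Remifentanil: 0.2 × 2.83 / 0.8 = 0.566 / 0.8 = 0.708

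**Reproducing the stated sizes (equal SDs).** The normal formula is n = 2(z_α + z_β)² / d². For propofol, one-sided: 2 × (1.645 + 0.842)² / 0.596² = 34.9. Two-sided: 2 × (1.960 + 0.842)² / 0.596² = 44.3. The t columns use the noncentral t distribution.

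| Measure | Stated n | One-sided, normal / t | Two-sided, normal (rounded up) / t | Power at 35, one-sided | Power at 35, two-sided |
|---|---|---|---|---|---|
| BIS SD | 26 | 25.8 / 27 | 33 / 34 | 89% | 82% |
| Propofol | 34 | 34.9 / 36 | 45 / 46 | 79% | 69% |
| Remifentanil | 24 | 24.7 / 26 | 32 / 33 | 90% | 83% |

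The stated sizes fit a one-sided calculation best, but only approximately. For propofol at 35 per group the noncentrality is 0.536 / (0.9 × √(2/35)) = 2.49 on 68 df. Power is 79.4% one-sided and 69.0% two-sided.

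**Sensitivity to the SD.** With 12 patients and approximate normality, the 95% CI for the SD runs from 0.9 × √(11/21.92) = 0.64 to 0.9 × √(11/3.816) = 1.53. Two-sided power at 35 per group is then about 93% at the lower end and 30% at the upper end.

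**Sensitivity to equal SDs.** The 12 patients say nothing about the SD under deep block. Assume it falls in proportion to the mean, so for propofol 0.8 × 0.9 = 0.72. The two-sided normal size is (0.9² + 0.72²) × (1.960 + 0.842)² / 0.536² = 36.3. The same calculation gives 25.6 for BIS SD and 25.7 for remifentanil. Two-sided propofol power at 35 per group is then about 77%.

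**Adjusting propofol for age.** Let R be the correlation of age with the maintenance average. The documents do not give R, so the values below are assumptions. The residual SD is 0.9 × √(1 − R²), and one degree of freedom is lost (67 left). Results for 35 per group:

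| R (assumed) | Two-sided power | One-sided power |
|---|---|---|
| unadjusted | 69% | 79% |
| 0.2 | 71% | 81% |
| 0.3 | 73% | 83% |
| 0.4 | 76% | 85% |
| 0.5 | 81% | 89% |

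Reaching 80% two-sided needs R of about 0.48. A simulation with 100,000 trials per setting, which allows for chance imbalance in age, gives slightly lower two-sided values (70%, 72.5%, 76%, 80%). If age is uninformative it gives 68.1% with ANCOVA against 68.8% for the t-test, so the cost is under one point.

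**The case against.** The strongest case against is that the t-test is valid and that nothing in the documents shows age to be related to maintenance propofol concentration. The infusion model is not named, so age may already be partly reflected in the measure. At R of 0.2 to 0.3 the gain is 2 to 4 points, far less than the uncertainty from an SD estimated in 12 patients. This stands. It makes age adjustment a cheap improvement in precision rather than the repair of an error. It does not touch the missing sidedness, which is a gap whatever R is.

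A second objection also stands. A reader might infer that the sizes can only have come from a one-sided calculation. That inference needs equal SDs. With the proportional-SD assumption, two-sided sizes of 25.6, 36.3 and 25.7 also lie near the stated 26, 34 and 24, although the one-sided equal-SD fit is closer.

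Third, nothing in the documents justifies adjusting propofol alone. The same model should serve all the continuous primary endpoints.

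A reader might also think of the propofol concentration at loss of consciousness as a covariate. The documents do not support it. It is judged clinically after allocation is known (section 6 f): "the anesthesiologist will only know to which group the patient was randomly assigned before induction starts"). Section 8 b) then uses it to set the first maintenance target and to limit protocol-driven propofol increases, so it is tied to the outcome itself.

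**Conclusion.** The point holds. The plan does not say whether its tests are one- or two-sided. With equal SDs at the plan's own values, 35 per group narrowly misses 80% power for propofol one-sided (79%) and falls clearly short two-sided (69%, with 46 per group needed). The shortfall is specific to propofol, since the other two measures stay above 80% two-sided.

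A reader might infer that the trial is simply underpowered for propofol, or that age adjustment would rescue it. Neither is shown. The planned test could be one-sided. Two-sided power could lie anywhere from about 30% to 93% given the 12-patient SD, and is about 77% if the SD falls with the mean. Adjustment reaches 80% two-sided only if R is about 0.48 or more, and the documents give no value. Nor is the t-test wrong: the case for ANCOVA is that it uses a value fixed before randomisation at almost no cost.

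**What to change.** 1. In section 11, state whether tests are one- or two-sided. In section 11 b), restate the propofol power at 35 per group to match, together with the uncertainty from the 12-patient SD and the equal-SD assumption.
2. Make the synopsis and section 6 a) agree on whether the drug concentrations are primary endpoints.
3. Prespecify ANCOVA with group and age for the continuous primary endpoints (propofol, remifentanil and BIS SD). Apply it whatever the baseline t-test on age shows. Report the adjusted difference with a 95% CI, and the unadjusted t-test alongside.

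This is a change of wording only, with no new data and no more patients. The statistical cost is one degree of freedom and, if age is uninformative, at most about one point of power. Section 11 f) requires changes to the statistical plan to go to the competent authorities before they take effect, so this should be settled before the analysis.
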